10.1.1 Early study termination

The study can be terminated at any time, for any reason, by Novartis. The investigator will be responsible for informing the Local Ethics Committee (LEC) of the early termination of the trial.

10.2 Information to be collected on screening failures

All patients who have signed informed consent but not entered into the next epoch will have the study completion page for the screening epoch, demographics, inclusion/exclusion, and serious adverse event (SAE) data collected. Adverse events that are not SAEs will be followed by the investigator and collected only in the source data.

10.3 Patient demographics/other baseline characteristics

All Baseline assessments should be performed prior to first study treatment administration. Patient demographic data to be collected on all patients include: date of birth, sex, race, ethnicity, and child-bearing potential (for females only), see the comments to the table 7-1.

10.4 Safety

Safety assessments will be performed as indicated in Table 6-1 and Table 6-2 and will be based on:

- Evaluation of all AEs and SAEs
- Physical examination, vital signs
- Laboratory tests analysis
- ECG results

10.4.1 Physical examination

A physical examination, including general appearance, will be performed as indicated in Table 7-1 and Table 7-2.

If indicated, based on medical history and/or symptoms, additional exams will be performed at the discretion of the investigator. Information for all physical examinations must be included in the source documentation at the study site.

10.4.2 Vital signs

Vital signs (including blood pressure and pulse measurements) will be assessed as indicated in Table 7-1 and Table 7-2.

DBP and SBP are measured after the patient has been sitting for 5 minutes, with their back supported and both feet placed on the floor, systolic and diastolic blood pressure will be measured twice, 1-2 minutes apart, using a validated device, with an appropriately sized cuff. In the event that a sufficiently large cuff is not available, a sphygmomanometer with an appropriately sized cuff may be used. The average of the two measurements will be entered into the eCRF.

Normal blood pressure will be defined as a systolic pressure of 90 to <120 mmHg, and a diastolic blood pressure of 60 to <80 mmHg under the measurement conditions outlined above. Notable blood pressure will be hypertension (systolic blood pressure of ≥ 140 mmHg and/or diastolic blood pressure of ≥ 90 mmHg) or hypotension (systolic blood pressure of <90 mmHg and/or a diastolic blood pressure of <60 mmHg).

A normal pulse rate will be defined as a rate of 60 to 100 beats per minute (bpm) under the measurement conditions outlined above. Notable pulse rates are a rate below 60 bpm (bradycardia) or above 100 bpm (tachycardia).

Whether action needs to be taken to address notable vital signs will be decided by the investigator, taking into account the overall status of the patient. No specific action is foreseen as part of the study protocol.

10.4.3 Height, weight, body mass index, waist circumference, waist/hip ratio

Height, body weight, body mass index, waist circumference, waist/hip ratio will be measured as indicated in Table 7-1 and Table 7-2. All parameters will be measured in indoor clothing, but without shoes. If possible, body weight assessments should be performed by the same study site staff member and using the same scale throughout the study.

10.4.4 Laboratory evaluations

A local laboratory will be used for analysis of all specimens unless noted otherwise.

10.4.4.1 General blood test

All indicators will be measured at planned visits according the Table 7-1 and Table 7-2.

10.4.4.2 Clinical blood chemistry

All indicators will be measured at planned visits according the Table 7-1 and Table 7-2.

10.4.4.3 Urinalysis

All indicators will be measured at planned visits according the Table 7-1 and Table 7-2.

10.4.4.4 Glycosylated hemoglobin

Glycosylated hemoglobin (HbA1c) assessment should be done at visit 1 and then after 12, 24, 36 and 48 weeks after the patient is included in the study, see Table 7-1 and Table 7-2.

10.4.4.5 Electrocardiogram (ECG)

A standard 12-lead ECG will be performed at visits according Table 7-1 and Table 7-2. At each visit when an ECG is done, the investigator must review, date and initial the tracing. The tracing must then be stored with the patient's source documents.

10.4.5 Appropriateness of safety measurements

The safety measures used in this study are reliable and relevant standard measures for patients with T2DM.

10.5 Other assessments

These include:

- Health economic supply form
- Survey on hypoglycemia

10.5.1 Health economic supply form

Special designed health economic (HE) supply form should be completed by investigator at the visits according Table 7-1 and Table 7-2.

This form includes the following aspects:

- Medical services for diabetes and it's complications over the last year
- T2DM drug therapy over the last year

- Related diseases drug therapy over the last year

Based on data from HE supply form health economic aspects will be analyzed. This analysis will be conducted separately after the final study report is completed.

10.5.2 Hypoglycemia Perspectives Questionnaire

The impact of T2DM on various aspects of patient's health-related quality of life will be assessed by the following validated instruments, each of which will be performed as indicated in Table 7-1 and Table 7-2.

- Health Questionnaire EQ-5D-3L
- Hypoglycemia Perspectives Questionnaire
- DTSQ

Doctor (investigator or acting as investigator) should fill out this survey based on what the patient says. The survey will be filled out in Russian before the patient attends the 1st visit of the study. The doctor should ask the patient to answer the questions and fill out the survey. The originals should be kept with other primary documents in the research center.

The patient should fill out the Diary of self-control in between the visits. The diary has teared-off pages where all data on food intake, the level of glucose before and 2 hours after the food intake and hypoglycemia therapy should be mentioned. Additionally, the patient should register in the Diary the change in glucose level, BP and pulse before and after physical exercises. Completed pages should be given to the doctor by the patient at each visit. In case of AEs or SAEs they should be registered according to the instructions of the Chapter 11. Reporting system is also described in Chapter 11.

11 Safety monitoring

Any serious adverse events will be reported to the Local Ethics Committee within 24 hours of the occurrence. All serious adverse events will also be reported to Novartis Drug Safety & Epidemiology (DS&E) within 24 hours of the investigator (or designee) being aware of the serious adverse event. Specific definitions of adverse events, and serious adverse events, are outlined below, along with reporting criteria required by Novartis.

Adverse events (AE)

Information about all AEs, whether volunteered by the patient, discovered by investigator questioning, or detected through physical examination, laboratory test or other means, will be collected and recorded on an Adverse Event Case Report Form and will be followed up as appropriate.

An AE is any undesirable sign, symptom or medical condition occurring after starting study treatment, even if the event is not considered to be part of lifestyle changes implied by this study.

Medical conditions/diseases present before starting study treatment will only be considered adverse events if they worsen after starting study treatment (any procedures specified in the

protocol). Adverse events (but not serious adverse events) occurring before starting study treatment but after signing the informed consent form will be recorded on the Medical History/Current Medical Conditions Case Report Form. Abnormal laboratory values or test results constitute adverse events only if they induce clinical signs or symptoms, are considered clinically significant or require therapy, and are recorded on the Adverse Events Case Report Form under the signs, symptoms or diagnosis associated with them.

As far as possible, each adverse event will also be described by:

1. the severity grade (mild, moderate, severe)
2. its relationship to the drug(s) of interest (suspected/not suspected)
3. its duration (start and end dates or if continuing at final exam)
4. whether it constitutes a serious adverse event (SAE)

Serious Adverse Events (SAEs)

Information about all serious adverse events will be collected and recorded on the Serious Adverse Event Report Form. To ensure patient safety each serious adverse event will also be reported to Novartis DS&E within 24 hours of the investigator learning of its occurrence.

An SAE is defined as an event which:

- Is fatal or life-threatening
- Results in persistent or significant disability/incapacity
- Constitutes a congenital anomaly/birth defect
- Requires inpatient hospitalization or prolongation of existing hospitalization, unless hospitalization is for:
 - Routine treatment or monitoring of the studied indication, not associated with any deterioration in condition (specify what this includes)
 - Elective or pre-planned treatment for a pre-existing condition that is unrelated to the indication under study and has not worsened since the start of the drug of interest
 - Social reasons and respite care in the absence of any deterioration in the patient's general condition
- Is medically significant, i.e., defined as an event that jeopardizes the patient or may require medical or surgical intervention to prevent one of the outcomes listed above e.g. may require treatment on an emergency outpatient basis for an event not fulfilling any of the definitions of a SAE given above and not resulting in hospital admission
- Transmission of infectious agent via medicinal product

No specific SAEs exempt from this reporting process are planned in this protocol.

Any SAE occurring after the patient has provided informed consent and until 4 weeks after the patient has stopped study participation will be reported. Serious adverse events occurring more than 4 weeks after study discontinuation will be reported to Novartis DS&E only if a relationship with any Novartis study therapy is suspected by the investigator.

Local Department of Pharmacovigilance (Clinical Safety) of Novartis Pharma in Russia

Phone: [REDACTED]

Fax: [REDACTED]

Email: [REDACTED]

Specialists in drug safety: [REDACTED]

As far as possible, each SAE will also be described by (but not limited to):

- Its duration (onset date = date of 1st signs or symptoms, and end dates)
- The seriousness criteria and severity if applicable (mild, moderate, severe)
- Its relationship to current investigational regimen (suspected / not suspected as judged by the investigator)
- The action(s) taken and investigation results if applicable
- Concomitant medication details
- Outcome

Notification of serious adverse events to Novartis Pharmaceuticals Drug Safety & Epidemiology (DS&E)

Each Serious Adverse Event (SAE) will be reported by the investigator to Novartis DS&E within 24 hours of learning of its occurrence, even if it is not felt to be related to study procedures or Novartis treatment. Follow-up information about a previously reported SAE will also be reported to Novartis DS&E within 24 hours of receiving it. If the SAE has not been previously documented (new occurrence) and it is thought to be related to study treatment, Novartis Drug Safety Department may contact the investigator to obtain further information.

If warranted, an Investigator Notification may be issued, to inform all investigators involved in any study with the same drug that this serious adverse event has been reported.

Reporting procedures

The investigator will complete the SAE Report Form, assess the relationship to study treatment/study procedures and send the completed and signed form by fax within 24 hours to Novartis DS&E. The original and the duplicate copies of the SAE Form, and the fax confirmation sheet will be kept with the case report forms at the study site.

Follow-up information will be sent to the same person to whom the original SAE Form was sent, re-stating the date of the original report. A new SAE Form will be used (stating that this is a “follow-up”). The follow-up report should describe whether the event has resolved or continues, if and how it was treated, and whether the patient continued or discontinued study participation. The form and fax confirmation sheet will be retained by the study site.

It is necessary to use a new form for SAEs reporting (it will be indicated there that new data is presented). While new form is presented it is necessary to report whether the previous case was resolved, treatment conducted or the SAEs is still ongoing. This form and fax copy will be kept in the research center.

Reporting about pregnancy

To ensure patient safety, each pregnancy in a patient will be reported to Novartis within 24 hours of learning of its occurrence. Pregnancy will be recorded on a Clinical Trial Pregnancy Form and reported by the investigator to the local Novartis Drug Safety and Epidemiology Department. Pregnancy follow-up will be recorded on the same form and will include an assessment of the possible relationship to the Novartis study drug of any pregnancy outcome. Any SAE experienced during pregnancy will be reported on the SAE Report Form.

12 Data review and database management

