7.1 Study design

This is a interventional, multicenter, non-randomized, parallel-group, opened designed study lasting during 12 months for approximately 130 patients with type 2 diabetes and obesity.

In spite of interventional study status, the drug therapy administration is carried out strictly in accordance with the approved instructions for medical use, only with the registered indications and in accordance with appropriate clinical practice. The decision on the drug therapy administration should be based only on the medical indications and on the judgment of a physician, but should not be dependent on the decision to include the patient in the study. The project includes unique method of weight management, specifically designed for the patients with type 2 diabetes. It includes five components:

- 1) Structured modified diet change;
- 2) Balanced and personalized physical exercises;
- 3) Cognitive behavioral support;
- 4) Intensive interactive medical assistance;
- 5) Group education.

An outline of the study design is presented in Figure 7-1. The full study lasts 12 months (1 month constitutes 4 weeks or 28 days). Patients from active group are monitored intensely during the first three months (on a weekly basis with acceptable window of visits +/- 1 day)

Nutritionist consultation	X																			
TE doctor/fitness trainer consultation	X																			
Demographic data ¹	X																			
Diabetes history ²	X																			
Relevant medical history / current medical condition ³	X																			
Group classes with endocrinologist		X	X	X	X	X	X	X	X	X	X	X	X							
Group classes with psychologist		X	X	X	X	X	X	X	X	X	X	X	X							
Group classes of nutrition		X	X	X	X	X	X	X	X	X	X	X	X							
Group classes of medical physical culture		X	X	X	X	X	X	X	X	X	X	X	X							
Physical examination	X				X				X			X	X	X	X	X	X	X	X	X
HbA _{1c}	X											X			X			X		X
FPG	X	X	X	X	X	X	X	X	X	X	X	X	X	X	X	X	X	X	X	X
Weight	X	X	X	X	X	X	X	X	X	X	X	X	X	X	X	X	X	X	X	X
BMI	X				X				X				X	X	X	X	X	X	X	X
Waist circumference	X				X				X				X	X	X	X	X	X	X	X
Waist/hip ratio	X				X				X				X	X	X	X	X	X	X	X
Blood pressure	X	X	X	X	X	X	X	X	X	X	X	X	X	X	X	X	X	X	X	X
ECG (standard 12-lead)	X												X							X
General blood pressure ⁴	X												X							X
Clinical blood chemistry ⁵	X												X							X
Urinalysis ⁶	X												X							X
AEs	X	X	X	X	X	X	X	X	X	X	X	X	X	X	X	X	X	X	X	X
Diaries of self-control	X	X	X	X	X	X	X	X	X	X	X	X	X	X	X	X	X	X	X	X

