Hypoglycemia questionnaires	X														X					X
Scale of Borg ⁷		X																		X
HE supply form	X				X				X				X	X	X	X	X	X	X	X

*Acceptable deviation for weekly planned visits (visits 2-13) is +/-1 day from the planned date, monthly visits (visits 14-22) is +/- 3 days from the planned date.

¹ Demographic indicators: age, gender, race.

² Date of diagnosis of diabetes, clinical symptoms.

Therapy for diabetes: insulin (type, dosage), insulin+oral hypoglycemic therapy (type, dosage), sulphonylurea (type, dosage), glinide (type, dosage), metformin (dosage), TZD (dosage), DPP4 (type, dosage), GLP1 (type, dosage), other type of treatment.

Complications of diabetes: cardio-vascular diseases, strokes, retinopathy, neuropathy, nephropathy, diabetic foot, other.

³ Concomitant diseases (cardio-vascular diseases, hypertension, eye diseases, vascular diseases of the brain, gastrointestinal tract diseases, respiratory diseases, liver and bile ducts diseases, kidney diseases, blood diseases, etc.)

⁴ General blood test: hemoglobin, leukocytes (+formula), erythrocytes, thrombocytes, ESR.

⁵ Clinical blood test: crude protein, cholesterol, lipids of low and high density, triglycerides, ALT, AST, KPhK, creatinine, GFR.

⁶ Urine analysis: color, transparency, relative density, traces of protein, sugar in urine, ketone bodies.

⁷ Scale of Borg (scale of individual perception of physical training) is part of Information card (Appendix 8).

Study period and parallel group study design allows achieving of primary end point.

The control group indicators should be coordinated with the indicators of patients in active group. The following should be taken into account when active group is being formed: correspondence of BMI and baseline HbA1c. The decision on whether the patient is included in active or control group is made by the doctor.

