7.6 Risks and benefits

The risk to subjects in this trial will be minimized by compliance with the eligibility criteria and study procedures, close clinical monitoring.

There are no therapy changes or innovations in this study. The drug therapy administration is carried out strictly in accordance with the approved instructions for medical use, only with the registered indications and in accordance with appropriate clinical practice.

The study is designed to establish for patients with T2DM and obesity the reduction of the body weight, improvement of glycemic and lipid metabolism, and reducing blood pressure level. We expect that the study can improve a QoL and reduce diseases complications in the study populations. Nvs survey on hypoglycemia will be used to assess the quality of life in patients (**Appendix 2**).

8 Population

The study is expected to include approximately 100 patients with T2DM and obesity. It is planned to have 100 patients in the active group who will be on active life style management; the control group will be 30 patients who will be matched with active group in terms of their indicators. Both groups will receive standard drug therapy for diabetes.

The control group should match the active group. The following criteria should be taken into account (criteria of inclusion and exclusion): match in BMI (<30; ≥30) and baseline HbA1c (<7.5; ≥7.5). The decision to include a patient into active or control group should be made by a doctor.

Drop-out of patients is expected for about 20% of patients compared with the originally included population. The drop-out criteria is three in a row missed group classes in the first 12 weeks of the study in active group.

The drop-out in control group is not expected.

Patients will be distributed among two participating research centers.

The study will be executed in two sites, the [REDACTED] in Moscow and the [REDACTED] in Kazan. The adult patients with T2DM (men and women at the age of more than 18 years) will be under the observation if they need in the active weight loss according to the physician's decision and if a doctor decides that the active approach is necessary.

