5.2 Secondary endpoints

- Body weight decrease expressed in percents and in absolute values in comparison with baseline at 3, 6, 9, 12 months of observation;
- Number (proportion) of patients achieved weight loss of at least 5% in comparison with baseline at 3, 6, 9 months of observation;
- Number (proportion) of patients achieved weight loss of at least 10% in comparison with baseline at 3, 6, 9, 12 months of observation;
- Changes of HbA1c and FPG levels expressed in percents and in absolute values;
- Number (proportion) of patients achieved decrease of HbA1c by at least 0.5% in comparison with baseline;
- Number (proportion) of patients achieved HbA1c $\leq 7\%$ at 12 months of observation;
- Blood pressure changes in absolute values in comparison with baseline;
- Number (proportion) of patients achieved decreasing of systolic and diastolic blood pressure levels by at least 5 mmHg in comparison with baseline;
- Changes of lipid profile (cholesterol, triglycerides, LDL, HDL) expressed in percents and in absolute values in comparison with baseline;
- Changes of waist circumference, waist-to-hip ratio;
- Changes of BMI;
- Assessment of changes by Hypoglycemia Perspectives Questionnaire for active group patients, as well as by perceived exertion rate with Borg scale.

6 Patients enrolled in the study

The study planned to include 130 patients with type 2 diabetes and obesity. In the active group, it was planned to recruit 100 patients, who will actively participate in lifestyle correction program; the control group will consist of 30 patients with T2DM, matching the active group patients by main parameters, who will to be managed in accordance with routine clinical practice for T2DM patients. The control group should be comparable to the active group with regard to the core baseline parameters.

When forming the control group, the following criteria should be taken into account (inclusion criteria in the study): BMI (<30 ; ≥ 30) and baseline HbA1c (<7.5 ; ≥ 7.5). The decision about inclusion of a patient in the active or control group is left at the discretion of the treating physician.

Dropout of 20% from initially enrolled population was considered by the study design. The patient's dropout from the study is defined as three consecutively missed classes within the first 12 weeks of observation in the active group. No dropout in the control group is assumed.

Patients are distributed between two sites participating in the study.

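### Protocol 10.5.2 has an unblinded doctor fill out the hypoglycaemia questionnaire, then a later sentence can be read as patient completion; one mode of completion should be fixed for a secondary quality-of-life result

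*Protocol*

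**What the plan says.** Protocol 10.5.2 lists three instruments (EQ-5D-3L, the Hypoglycemia Perspectives Questionnaire and DTSQ) and then speaks of a single survey. On who completes it, the paragraph gives two instructions:

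- "Doctor (investigator or acting as investigator) should fill out this survey based on what the patient says"
- "The doctor should ask the patient to answer the questions and fill out the survey" (two sentences later)

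The setting is a "non-randomized, parallel-group, opened designed study lasting during 12 months" (Protocol 7.1). SAP section 4 marks randomization and blinding as not applicable. On group membership, Protocol section 7 states after the visit schedule: "The decision on whether the patient is included in active or control group is made by the doctor". Protocol section 8 repeats this, and SAP section 6 says: "The decision about inclusion of a patient in the active or control group is left at the discretion of the treating physician".

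On use, Protocol 7.6 states: "Nvs survey on hypoglycemia will be used to assess the quality of life in patients". The SAP words the endpoint as "Assessment of changes by Hypoglycemia Perspectives Questionnaire for active group patients, as well as by perceived exertion rate with Borg scale" (SAP 5.2). SAP section 13 computes subscale means at Visit 1, week 24 and week 48 and describes them, with changes from baseline, by group and visit.

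**The concern.** A quality-of-life instrument is meant to capture the patient's own view. When a member of the study team writes down the answers, two influences enter: the patient speaks to someone involved in the care, and the recorder turns speech into a response category. In an open study the recorder can know which group the patient is in.

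The second instruction adds a separate problem. One site may have the doctor write while the other hands the form to the patient, or the mode may change between baseline and follow-up. Both readings comply with the text.

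At stake is the secondary objective of improved quality of life (Protocol 6.2, SAP section 1). The SAP presents these scores without a model, so any artefact of recording passes straight into the tabulated means and changes.

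**Working it through.** The plan states no expected effect, SD or power for the questionnaire, and its sample size concerns weight. There is no figure to reproduce, so the check is a reading of the passages. I assume that the sponsor's hypoglycaemia survey named in Protocol 6.2 and 7.6 is the Hypoglycemia Perspectives Questionnaire, because the SAP uses that name in the matching objective.

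1. **Who completes the form.** The first instruction names the doctor. In the second, the verb for filling out can attach to the doctor or to the patient. No other section settles it.

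2. **Whether the recorder can know the group.** The design is open and no independent interviewer is provided for. By weeks 24 and 48 nothing conceals who has been in the program.

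3. **When recording moves the result.** Let r be the average shift that the mode of completion adds to a score.
   - Observed change in one group = true change + (r at follow-up − r at baseline).
   - Observed group difference in change = true difference + (that shift in the active group − that shift in controls).
   - If r is the same at every visit and in both groups, both extra terms are zero.
   - The result moves only if r differs by visit or by group. Knowledge of group can make it differ, and so can an unsettled mode of completion.

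4. **When the form is completed.** The paragraph's one explicit timing sentence puts completion before the first visit and otherwise refers to the schedule tables. SAP section 13 gives three administrations. Inclusion criterion 1 (Protocol 8.1) requires consent before any assessment. A rule on mode should therefore cover all three administrations and place the first after consent.

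5. **Which instruments are covered.** Three are listed, the instruction is singular, and SAP section 13 analyses only the hypoglycaemia questionnaire.

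6. **Whether patient completion is practical here.** Patients already keep the self-control diary (Protocol 10.5.2). Active patients fill out the Information card, which contains the Borg scale (Protocol section 10). The originals of the survey are already to be kept with the site's primary documents, which suits a paper form.

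7. **What is not affected.** The primary endpoint is a loss of at least 5% of measured body weight at 12 months (SAP 5.1) and does not use the questionnaire.

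**The case against.** The strongest reply is that the protocol asks the doctor to write down what the patient says, not to judge it, and sets the same rule for everyone; a constant mode effect cancels (step 3). The questionnaire is one secondary measure, and the objective also names the Borg scale. The documents call the instruments validated but do not say for which mode of completion. All of this stands, and it limits the weight of the point. It does not resolve the two instructions, and it does not make the recorder's effect constant in an open study.

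A reader might infer four stronger things that the documents do not support:

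- **A false-positive rate.** One could assume a recording shift and put it through a two-sided 5% test. With 100 × 0.8 = 80 active patients and 30 controls, SE = √(1/80 + 1/30) = 0.214 SD. A shift of 0.1 SD is 0.47 SE and gives about 7.5%; 0.5 SD is 2.34 SE and gives about 65%. The result is simply the assumed shift restated, and the SAP plans no such test.
- **That self-completion would avoid the bias at no cost.** It takes out the recorder only. Patients still know their group, a doctor chose it, and some items may be skipped.
- **That weekly contact in the active group drives the follow-up scores.** Active visits are weekly only for about the first three months. By weeks 24 and 48 they are monthly, against quarterly visits for controls.
- **That the doctor who chose the group also fills out the form.** The documents do not say so. The argument needs only an unblinded recorder.

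**Conclusion.** The point holds as a weakness in how a secondary outcome is collected. Protocol 10.5.2 assigns completion to an unblinded doctor and then leaves room for the opposite reading, so recorder influence and a mixed mode can both enter the quality-of-life result.

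The size cannot be derived from the documents. The result exposed is the descriptive tabulation by group and visit, including the active group's change from baseline, which is how SAP 5.2 words the endpoint. The primary weight result is untouched. The change is worth making because the remedy is specific and cheap, not because the study's main conclusion depends on it.

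This rests on two assumptions: that the hypoglycaemia survey and the Hypoglycemia Perspectives Questionnaire are the same instrument, and that the form can be completed by the patient. The second should be confirmed against the instrument's own instructions.

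**What to change.** In Protocol 10.5.2, replace the two instructions with one rule that applies to both groups, both sites and every administration (Visit 1 after consent, week 24, week 48):

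- The patient completes the form on paper before seeing site staff.
- Staff check only for skipped items.
- Any help given, for example with reading, is recorded in the eCRF.

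State which of the three listed instruments the rule covers. In SAP section 13 and Table 10.1, label the result as open-label and descriptive. If forms have already been collected, report the mode that was used.

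The cost is a few lines of protocol text, an eCRF entry for assistance and perhaps a few more skipped items. No visit, sample size or primary analysis changes.
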